Traditional suture-based fixation is known to cause significant patient discomfort, predominantly at the site of skin suture fixation, where any pull on the drain tubing is transmitted to a focal point on the skin. Over time, this can result in significant skin irritation, inflammation and pain, skin erosion, loosening of the drain, suture failure, and possibly even early, unintended loss of the drain. Early loss of a drain, in turn, can lead to complications of seroma and/or infected abscess. In a survey of 40 Wake Forest Plastic Surgery Patients with drains, patients asked were to rate their experience with surgical drains compared to their expectations on a sliding scale. The majority of patients reported experiences that were worse than or as expected (Figure 1). When specifically asked about irritation at the drain site, 33 of 40 patients rated comfort and pain as worse than

or as expected (Figure 2). With the known negative patient experiences associated with suture-based drain securement, there is a need for novel drain securement techniques and devices that can improve patient comfort and drain security.

The K-Lock® Device is a novel sutureless drain securement device that may improve patient experiences with surgical drains. The K-Lock Device is an FDA Class I device exempt from 510k requirements.

OBJECTIVES:

To evaluate the feasibility, safety and efficacy of a novel suture-less drain securement device (K-Lock) via direct comparison to suture-based techniques.

To evaluate patient satisfaction with their surgical drain sites post operatively.

DESIGN:

Randomized controlled trial

SETTING:

Academic Medical Center

SUBJECTS SELECTION CRITERIA:

Inclusion Criteria:

Age 18 or older

Patient of the Department of Plastic and Reconstructive Surgery

Able to sign English language Consent form

Undergoing any of the following procedures requiring placement of 2 or more drains (preferably bilateral) including:

- Breast reconstruction
- Bilateral Breast Reduction
- Abdominoplasty
- Body Contour surgery (e.g. panniculectomy, brachiplasty, thighplasty)

Exclusion Criteria:

Patients with unilateral drain placement Unable to sign English language consent form Allergy to Tegaderm Dressing Allergy to skin adhesives

SAMPLE SIZE:

We plan to enroll 40 patients allowing analysis of 80 (20 paired) drain sites: 40 prototype drain securement sites and 40 suture-based drain securement sites.

INTERVENTIONS AND INTERACTIONS:

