Patients will be randomized to either A) left side K-Lock with right side suture-based technique or B) right side K-Lock with left side suture-based technique. Randomization will occur before study initiation with group A or group B being assigned to a study enrollment number.

Preoperatively:

The novel suture-less prototype device will be described and/or demonstrated to the patients, and the rationale for its development will be explained. They will have opportunity to ask questions and then they will be invited to participate in the study.

Written informed consent will be obtained.

Intraoperatively:

Surgical drains will be placed per the usual routine of the surgeon. However, prior to definitive fixation, the drains will be temporarily secured to the skin with a towel clamp and covered and/or positioned out of the way to allow for closure of surgical incisions. Definitive drain fixation will occur when all of the pertinent incisions are closed and dressed. At that time, each drain will be secured according to the randomization scheme.

The amount of **time it takes to secure and dress each drain will be recorded** using a time-stamped video (e.g. iphone). No identifying data/information will be recorded, only the zoomed field pertinent to drain securement. For the prototype drain securement device, the 'video clock' will be started when the device is passed to the surgeon and stopped when the device/dressing is attached in place. For the standard suture-based technique, the 'video clock' will be started when the suture is passed to the surgeon and will be stopped when the dressing has been placed and secured. Use of a Biopatch with the drain will be up to the surgeon's preference. The standard dressing for the suture-based techniques will include a split 4 x 4 dressing covered with a tegaderm. All dressing materials must be ready and available prior to handing the surgeon the suture/device.

Postoperatively:

The time until drain removal will be recorded for both groups.

On postoperative visit(s) on which a drain is removed, patients will complete a **survey** about their experience with the pertinent securement method/drain site.

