Feasibility and **ease of use** of the novel drain device will be evaluated by evaluation of video recordings, qualitative feedback obtained from surgeons and/or O.R staff and nurses that handle and observe use of the device. Any failed application of the device will specifically be noted. In the event that a test device will need to be replaced for continued drain securement because the device has become loose or otherwise fouled, the replacement process will be performed by clinic staff using the IFU for such, and will be video recorded

Safety of the novel drain device will be evaluated by inspecting device sites for instances of skin irritation at each office visit and at the time of drain removal, including photographs of drain sites immediately before and after removal. It will also be assessed by feedback obtained in the patient surveys.

Postoperative review of patient charts will collect the following information up to 1 month from the removal of a subject's final drain:

- Date of drain removal (i.e. duration of drain)
- Accidental vs Planned drain removal
- Loosening of the drain
- Any need for new device/new suture material to secure drain
- Reinsertion of drain
- Patient calls to triage regarding drain issues/concerns and the estimated or actual time/effort devoted to each issue/concern by clinic staff
- Photos of the drain site at time of removal

As a follow-up to previous study activities, subjects will be contacted either by phone or at future clinic visits to gauge their interest in further participation. Subjects will be asked to have pictures taken of their drain sites and to fill out a survey to measure their satisfaction with their surgical drain sites further out from their procedures. Pictures will be attained at a scheduled research visit or a regular clinic visit if possible. A blinded evaluator will view the photos to assess in addition to the subject's self-reported outcomes. The tool the subjects will complete is the Patient and Observer Scar Assessment Scale (POSAS).

OUTCOME MEASURES:

Primary:

Feasibility

Secondary:

Safety

Satisfaction

ANALYTICAL PLAN:

Results will be analyzed initially using descriptive statistics. Comparison between groups will be done using chi square tests for proportions, and t-tests or ANOVA procedures for continuous variables. Regression analysis will be performed to identify independent outcome predictors. Other inferential statistical analysis will be conducted as appropriate.

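### Does the removal-visit survey need an added same-day rating of both drain sites to give a fair satisfaction comparison?

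*Combined protocol and SAP*

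**What the plan says.** The design is a within-patient comparison: "Patients will be randomized to either A) left side K-Lock with right side suture-based technique", or the reverse. One stated objective is "To evaluate patient satisfaction with their surgical drain sites post operatively", and OUTCOME MEASURES lists satisfaction as secondary, after feasibility as primary.

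Two survey contacts bear on satisfaction, both described in the postoperative text:

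- **Removal-visit survey.** "On postoperative visit(s) on which a drain is removed, patients will complete a" survey "about their experience with the pertinent securement method/drain site". The trigger is removal of a drain, and the subject is the site concerned. The wording allows one removal visit or several.
- **Later follow-up survey.** Subjects who agree to further participation have their drain sites photographed and complete the POSAS. No time point is fixed, and the instrument is a scar scale.

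Timing is recorded: "The time until drain removal will be recorded for both groups", and the chart review lists "Date of drain removal (i.e. duration of drain") together with whether removal was accidental or planned. Sites are also photographed around removal ("including photographs of drain sites immediately before and after removal"). The patient survey is item 1 of the APPENDIX, but the form is not in the public document. Its scale, its recall period and any question about the other side are therefore unknown.

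**The concern.** When each patient serves as their own control, one expects the two sites to be rated under like conditions. Here the rating day is set by each drain's own removal. If the drains come out at separate visits, one site is judged earlier after surgery and after less wear than the other.

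The BACKGROUND section supplies a possible link to the method. It says suture fixation can cause irritation and pain that build over time, and "possibly even early, unintended loss of the drain". If the method shifts the removal day and ratings change with time, the difference in ratings mixes how the securement feels with how long it stayed on. The recorded dates would reveal the gap in days, but they cannot supply a rating on a day when the patient was not asked. The text also does not say when the survey is completed if a drain is lost between visits. A same-day rating of both sites would be cheap, and it could not be recreated after the trial.

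**Working it through.** **1. The plan's own figure.** SAMPLE SIZE gives 40 patients and 80 sites. 40 × 2 = 80, which reproduces. One site per method per patient gives 40 pairs; the 20 pairs mentioned in the same sentence do not follow from this. 40 pairs are used below, with 20 as a check. No alpha, power, effect size or SD is stated.

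**2. What staggered removal does under randomised side.** There are two cases.

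- *The gap in removal days is unrelated to the method.* Its mean is zero, so it adds noise and no bias. Assume a 0-100 rating, an SD of paired differences of 20, a true difference of 10, 40 pairs and two-sided alpha 0.05. Power is then 86.9% with no gap. With a gap SD of *s* days and a drift of *b* points per day, the SD becomes √(20² + (*b*·*s*)²):
  - *b* = 0.5, *s* = 3: SD 20.06, power 86.8%
  - *b* = 2, *s* = 5: SD 22.36, power 78.8%
- *The method shifts removal day.* The end-of-wear difference then includes that shift. It is still an unbiased estimate of total experience up to removal, but it differs from a same-day difference.

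**3. Size of that difference.** Gap = drift per day × mean shift in rating day. It is zero if either factor is zero. All inputs are assumptions: a share of one method's drains is lost and rated 7 days early, and drift is 1 or 2 points per day.

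| Share lost (of 40) | Mean shift, days | Gap, points | Gap ÷ 6.40 | Chance of p < 0.05 if same-day difference is 0 |
|---|---|---|---|---|
| 5% (2) | 0.05 × 7 = 0.35 | 0.35 to 0.70 | 5% to 11% | 0.051 to 0.055 |
| 10% (4) | 0.10 × 7 = 0.70 | 0.70 to 1.40 | 11% to 22% | 0.055 to 0.072 |
| 20% (8) | 0.20 × 7 = 1.40 | 1.40 to 2.80 | 22% to 44% | 0.072 to 0.139 |

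The half-width is t(0.975, 39) × 20/√40 = 6.40 points. It is 4.80 at SD 15 and 8.00 at SD 25, and with 20 pairs at SD 20 it is 9.4. If lost drains are rated only 3 days early, the shifts are 0.15, 0.30 and 0.60 days and the gap is 0.15 to 1.2 points. A gap of 6 points needs a 3-day mean shift across all pairs at 2 points per day (3 × 2 = 6), and nothing in the documents supports that. The rejection rates in the last column are not false positives for total experience up to removal.

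**4. What an added same-day rating would supply, by type of patient.**

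- *Both drains removed at one visit.* Both were placed at the same operation, so the existing survey already gives a same-day, equal-wear pair. The extra rating largely repeats it.
- *One drain lost early.* These pairs generate every gap in the table. A rating taken after the loss compares a site with a drain to one without, so wear is still unequal. Setting such pairs aside selects on something the method may affect. It also widens the half-width from 6.40 to 6.77 (36 pairs) or 7.21 (32 pairs).
- *Planned removals at different visits.* Here the extra rating does give something new. The documents do not say how common this is, or that the method affects it.

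**The case for a change.** The best case for a change is that the added rating costs little and the chance to collect it passes. The visit already takes place, a photograph is already taken just before removal, and no arm, visit or sample size would change. Pairs from patients whose drains happen to leave together are not a randomised subset, because joint removal may itself depend on the method. They cannot fully stand in for a planned pair in everyone. The POSAS survey does not fill the gap either: it is voluntary, untimed and about scars, so it does not measure comfort during wear.

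All of that stands as fact, and so does the narrower observation that no common rating day is set. It does not show that the planned comparison is wrong. The objective asks about satisfaction after surgery, not satisfaction at equal wear. If a method leads to earlier or later removal, that is part of what the patient experiences with it. A survey about experience with a site may also be retrospective over the whole wear period, in which case a daily drift in a momentary rating is not the right model. The unseen form prevents settling this, and it also prevents saying that no side-by-side question exists. In addition, patients may have more than two drains, so a rating of both sites would itself need defining.

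**Conclusion.** No change to the plan follows. The removal-visit survey yields a valid randomised comparison of experience up to removal. An equal-wear comparison is a second question that the protocol does not pose, and statisticians could reasonably differ on whether to add it.

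On assumed inputs the two differ by 0.35 to 2.8 points against a half-width of 6.4, and by close to nothing if few drains are lost. These figures rest on a 0-100 scale (borrowed from the earlier 40-patient survey in BACKGROUND, not known to be the trial's), SD 20, 40 pairs, losses in one method only, and a drift of 1 to 2 points per day. None of these comes from the trial's own plan, so direction and size remain unknown.

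The part that matters for interpretation is already covered. Removal dates and accidental versus planned removal are collected, so the analyst can report the within-patient gap in removal days beside the satisfaction result and describe that result as experience over the wear period. The unstated survey timing after a loss between visits is a small gap that study staff can handle by recording when the form was completed.

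### The drain-experience survey is tied to a clinic removal visit, so a drain lost accidentally elsewhere triggers no rating for that site

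*Combined protocol and SAP*

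**What the plan says.** All references are to the combined protocol and SAP.

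- **Trigger and scope.** INTERVENTIONS AND INTERACTIONS (Postoperatively): "On postoperative visit(s) on which a drain is removed, patients will complete a" survey "about their experience with the pertinent securement method/drain site". No other trigger for this survey is given.
- **Accidental loss is foreseen.** BACKGROUND, RATIONALE AND CONTEXT names "early, unintended loss of the drain" as a possible result of suture fixation. The chart-review list includes "Accidental vs Planned drain removal", as well as loosening, re-securement and reinsertion.
- **Use of the survey.** Safety is assessed by "inspecting device sites for instances of skin irritation at each office visit and at the time of drain removal", and then: "It will also be assessed by feedback obtained in the patient surveys". Satisfaction is a secondary outcome, but the documents do not say which survey supplies it.
- **Other survey.** A later follow-up uses the POSAS, for subjects who are interested in taking part further.
- **Eligibility and size.** Patients need at least two drains, and the exclusions include "Patients with unilateral drain placement". SAMPLE SIZE plans "40 prototype drain securement sites and 40 suture-based drain securement sites".
- **Missing ratings.** ANALYTICAL PLAN gives no rule for them.

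**The concern.** A securement method exists to keep the drain in place. A site whose drain came out by accident may be one where the method failed, and the patient's view of that site is among the most informative in the trial. The stated trigger leaves out exactly these sites when the loss happens away from clinic. Whether a rating is missing may then depend on the performance being compared. If lost sites would have been rated worse, the method that lost more drains would look better among the surveyed sites than it was.

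Each patient carries one method on each side, so one missing rating also removes that patient's within-patient contrast. At stake are the experience comparison, the survey-based part of safety, and satisfaction in so far as it draws on this survey.

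**Working it through.** The documents state no figure on this point (no loss rate, effect size, standard deviation or power), so there is none to reproduce. The check has two parts.

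**1. Does any text close the gap?**

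- *Removal visit for the other drain.* This will usually follow, since unilateral placement is excluded. But the survey concerns the pertinent site which, read strictly, is the drain removed at that visit.
- *Reinsertion.* A reinserted drain later removed in clinic would be surveyed. A lost drain that is not reinserted would not.
- *POSAS follow-up.* It needs no removal visit, but it is voluntary, later and a scar scale. It does not rate the experience of having the drain in place.
- *Chart review.* It counts the loss but holds no patient rating.

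No supplied text calls for a make-up survey.

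**2. How much could be left open?**

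Input: 40 sites per method (SAMPLE SIZE). That section gives 20 as the number of pairs, whereas 40 patients with one site per method make 40 pairs; the 40 sites per method used here are stated directly. If patients contribute more than two drains, the denominators grow.

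*Outer limits for a yes/no item.* With x observed yes answers and k unsurveyed sites, the proportion over all 40 lies between x/40 and (x + k)/40, a width of k/40. The k values are assumptions.

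| k | Width (percentage points) |
|---|---|
| 0 | 0 |
| 1 | 2.5 |
| 3 | 7.5 |
| 6 | 15 |

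The K-Lock minus suture difference lies between [xK − (xS + kS)]/40 and [(xK + kK) − xS]/40, a width of (kK + kS)/40. With 1 and 1 this is 2/40 = 5 points; with 1 and 3 it is 4/40 = 10 points. These are outer limits, not expected bias.

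*Illustration for a mean rating.* Let q be the share of a method's sites that go unsurveyed, and D the amount by which those sites would have scored below the surveyed ones. The surveyed mean then exceeds the full mean by qD. With the same D for both methods, the difference shifts by (qK − qS)D. At assumed shares of 15% and 5%, and D of 10 to 30 points on an assumed 0–100 scale, the shift is 0.10 × 10 = 1.0 to 0.10 × 30 = 3.0 points in favour of the method that lost more drains. With equal shares it is 0.

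*Complete pairs.* If losses are independent, the expected number is 40(1 − qK)(1 − qS): 40 × 0.95 × 0.95 = 36.1 at 5% on both methods, and 40 × 0.85 × 0.95 = 32.3 at 15% and 5%.

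**The case against.** The strongest reply is that little of consequence may depend on this survey. The second objective, on satisfaction with the drain sites, is worded much like the POSAS follow-up, which no removal visit triggers; satisfaction might come from there alone. Safety rests first on inspection at every office visit, and chart review captures the failure itself. The Patient Survey is Appendix 1 and is not shown, so it may already say when it is given. Nothing forbids asking about a lost drain at a later visit. The k/40 width would apply to any missing yes/no item, and no such item is shown. Finally, late or phone ratings would fall mainly on failed sites, mixing recall and mode with securement failure.

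Much of this stands as limits. The link to satisfaction is unproven, the loss event is recorded, Appendix 1 could hold an instruction, and the widths say nothing about likely bias. It does not remove the point. The only stated rule, followed as written, omits the patient's rating where securement may have failed, and POSAS does not measure the same thing. That staff could ask anyway does not make the plan require it. A rating with a known delay and mode is more useful than none.

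**Conclusion.** The concern holds. As written, a drain lost outside clinic triggers no experience survey for its site, and the resulting missing ratings may depend on how the securement method performed. Each such site is 2.5% of a method's planned ratings. Neither size nor direction of bias follows from the documents; the figures above rest on assumed numbers of losses and assumed rating gaps, and if no drain is lost outside clinic nothing is lost.

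The effect is confined to the patient's rating: the experience comparison, the survey-based part of safety, and satisfaction if it uses this survey. It is a worthwhile, low-cost improvement rather than a threat to the trial as a whole. Confidence is medium, mainly because Appendix 1 could not be read.

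**What to change.** Replace the trigger with wording such as:

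> The patient completes the survey for each drain site at the visit where that drain is taken out or, if it is lost or removed outside clinic, at the first visit or call afterwards, including the removal visit for the other drain.

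Record the date and mode (clinic or phone) of every survey not completed at removal. Report survey completeness by method and by accidental versus planned removal. If Appendix 1 already contains such a rule, state it in the protocol text.

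The cost is one extra form at the other drain's removal visit, or a short call, for each drain lost outside clinic. Triage calls about drains are already recorded through chart review, which can help identify these cases, although they are not now a study contact. The downside is somewhat later recall and a possible phone-versus-clinic difference for lost drains. Recording date and mode makes both visible but does not remove them; using the other drain's removal visit where possible keeps phone ratings to a minimum. Clinical management does not change.

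### No clearly masked assessment of skin irritation at drain removal, although the plan already collects after-removal photographs and has a blinded evaluator

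*Combined protocol and SAP*

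**What the plan says.** The relevant text is in Interventions and Interactions, under Postoperatively.

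- **Inspection.** "Safety of the novel drain device will be evaluated by inspecting device sites for instances of skin irritation at each office visit", and again when the drain comes out, "including photographs of drain sites immediately before and after removal". The plan names no assessor, gives no grading scale and states no masking.
- **Surveys.** A second safety source follows: "It will also be assessed by feedback obtained in the patient surveys".
- **Chart review.** The list of collected items includes "Photos of the drain site at time of removal", again with no reader or scale.
- **Follow-up.** Participants are contacted again to see whether they wish to take part further. Those who do have new pictures taken and "fill out a survey to measure their satisfaction with their surgical drain sites further out from their procedures". In that paragraph the plan says "A blinded evaluator will view the photos to assess in addition to the subject's self-reported outcomes". The instrument named there is POSAS, a scar scale.

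Each patient has K-Lock on one side and suture on the other (Interventions and Interactions, opening paragraph). The device and the reason for developing it are explained to patients before surgery (Preoperatively). Safety is a secondary outcome and feasibility is primary (Outcome Measures). The Objectives call for a direct comparison with suture-based techniques.

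**The concern.** Whether skin is irritated is a matter of judgement. Anyone who inspects a site with the drain in place can see which method holds it. The Background sets out the expectation that sutures irritate the skin and that K-Lock may improve the experience, and patients are told why the device was developed. An assessor or patient who shares that expectation may call irritation less readily on the K-Lock side. Because the two methods are compared within the same patient, a one-sided shift of this kind goes straight into the reported difference.

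The masking that is clearly planned applies to late appearance, in those who volunteer for follow-up. It does not clearly reach irritation at removal, which is the named safety measure. Yet the after-removal photograph is taken once the securement is gone, and so is the natural material for a masked reading.

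**Working it through.** The plan gives no figure to reproduce on this point. It states no irritation rate, alpha, power or effect size. The check is first textual and then a numerical illustration.

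**1. Which irritation data are masked?**

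| Source | Timing | Method hidden from the assessor? |
|---|---|---|
| Inspection | Office visits and removal | No masking stated; securement visible while the drain is in place |
| Patient survey | Visit at which a drain is removed | No; patients are told about the device |
| Photograph before removal | Removal | No reader named; shows the securement |
| Photograph after removal | Removal | No reader named; securement gone, marks may remain |
| Follow-up pictures | Later, optional | Yes, blinded evaluator named; the instrument in that paragraph is a scar scale |

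The only row with stated masking is not about irritation at removal.

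**2. How large could the effect be?**

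Inputs from the plan: 40 patients, one site per method each, so 40 × 2 = 80 sites and 40 pairs. (The Sample Size section also says 20 paired, which does not agree with 40 patients treated on both sides. That is a separate point.)

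Assumptions, none of them in the plan:
- the true irritation rate p is equal on both sides and independent within patient;
- the open assessor misses a share u of true irritation on the K-Lock side only;
- the test is an exact two-sided McNemar test at 0.05, which suits pairs but is not the test named in the Analytical Plan.

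Formulas:
- recorded K-Lock rate = p(1 − u); recorded suture rate = p; false difference = pu
- discordant pair, irritation on K-Lock only: a = p(1 − u)(1 − p)
- discordant pair, irritation on suture only: b = p[1 − p(1 − u)]
- the number of discordant pairs is binomial(40, a + b); given that number, the K-Lock-only count is binomial with probability a/(a + b)
- false rejection = total probability of all outcomes with exact McNemar p-value at or below 0.05

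Example, p = 0.40 and u = 0.50: recorded rates are 0.20 and 0.40, a = 0.20 × 0.60 = 0.12, b = 0.40 × 0.80 = 0.32. The expected number of discordant pairs is 40 × 0.44 = 17.6, and false rejection is 40.4%.

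| True rate p | u = 0 | u = 25% | u = 50% |
|---|---|---|---|
| 10% | 1.7% | 2.2% (false difference 2.5 points) | 4.4% (5 points) |
| 20% | 2.5% | 4.8% (5 points) | 14.6% (10 points) |
| 40% | 3.0% | 10.6% (10 points) | 40.4% (20 points) |

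At a true rate of 10%, even missing half of the K-Lock cases leaves false rejection below 5%. The large figures need both common irritation and marked under-calling.

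**The case against.** Several points on the other side are sound.

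- **A reader might infer that irritation is judged only by staff.** The documents do not support that. Patient surveys also contribute to safety, and the inspector is not named. That the inspector can see the method is a sound inference from the design, not stated text. The surveys do not cure the problem, because they are unmasked.
- **A reader might infer that a masked reading of the removal photographs is ruled out.** It is not. "A blinded evaluator will view the photos to assess" stands in the follow-up paragraph and most naturally means the later pictures, but the wording does not exclude the removal photographs. The plan is unclear, and on its natural reading leaves them out.
- **A reader might infer that the photograph score should replace the inspections as the main irritation outcome.** That would be a poor trade. Inspections cover every office visit. A single photograph misses irritation that came and went earlier, and it may not exist where a drain was lost by accident.
- **Masking may be incomplete.** Suture holes or adhesive marks can reveal the method and may themselves be part of what is graded, so cropping cannot always remove them. This limits the gain, but partial masking that is measured is still better than none.
- **An irritation scale would have to be written.** POSAS does not serve. This is a real but small cost.
- **The stakes are modest.** Safety is secondary, no formal safety hypothesis or alpha is stated, and descriptive statistics come first. Bias in the recorded rates matters for a descriptive comparison too, but the primary outcome is not touched.

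**Conclusion.** The point stands as follows: the plan has no clearly masked assessment of skin irritation at drain removal. Inspection is done with the method visible, the surveys are unmasked, and the blinded evaluator is named only in connection with the optional later pictures. The named safety comparison is therefore open to observer bias that the plan already has most of the means to check.

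The possible size ranges from negligible (2.2% false rejection at a 10% true rate and 25% under-calling) to serious (40.4% at a 40% rate and 50% under-calling), against 1.7% to 3.0% without bias. This range rests entirely on assumed rates, independent sides, 40 complete pairs and a test that the plan does not name. It shows what could happen and does not estimate what will. The documents contain no evidence that such bias is present. The change is worth making, but the feasibility outcome does not depend on it.

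**What to change.** Add to the Postoperatively section and the Analytical Plan:

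1. The same blinded evaluator also grades the after-removal photographs of both the K-Lock and the suture site. Photographs are cropped, labelled by code and presented in random order.
2. Grading uses a simple irritation scale fixed in advance, separate from POSAS.
3. The evaluator records a guess of the method for each photograph, and the share of correct guesses is reported.
4. The result is reported as a prespecified masked comparison of irritation at removal, alongside the inspections at office visits and at removal. Those inspections are kept in full and not demoted.
5. The inspection assessor and scale are named and applied to both sides, since the safety sentence speaks only of device sites.
6. The number of sites with no after-removal photograph is reported for each method.

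The cost is about 80 readings (40 patients × 2 sites) by an evaluator already in the plan, and the writing of a short scale. No visit or procedure is added. The remaining weakness is partial unmasking by suture or adhesive marks, which item 3 makes visible.
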